7.0 Statistical Considerations

7.0 Primary measures and analyses:

- 7.0.1 Bone Resorption: NTX
- 7.0.2 Bone Formation: BAP

Since the primary objective of this pilot study is to gather preliminary efficacy and feasibility data for the development of a planned career development grant application, the primary analyses will consist of calculating mean change scores (i.e., baseline assessment minus final assessment) and standard deviations for the two variables above. In addition, a paired-sample t-test will be used to calculate the differences between the baseline and end of trial value for both BAP and NTX. An independent t-test will be used to calculate the difference between the baseline and end of trial value for both BAP and NTx between the trial arms. Lastly, ANCOVA models will be used for BAP and NTx with the addition of relevant covariates collected during the study. Results of these two analyses will be interpreted cautiously because of the limited sample size.

7.1 Secondary measures and analyses:

- 7.1.1 Physical Activity: ACLS and Pedometer
- 7.1.2 Aerobic Capacity: VO2max Treadmill Test
- 7.1.3 Muscular Fitness: Handgrip Dynamometer and 7-10 Repetition Maximum
- 7.1.4 Muscle Mass: Bioelectrical Impedance Analysis
- 7.1.5 Since the secondary aims relating to physical activity, aerobic capacity, muscular fitness, and muscle mass, respectively, are intended to gather preliminary efficacy data for the development of a planned K07 submission, the secondary analyses will consist of calculating mean change scores (e.g., baseline assessment subtracted from the final assessment, and baseline subtracted from the follow-up assessment), standard deviations, and correlations on these variables for the two study arms. Additional exploratory analyses will use mixed effects models, to compare mean bone health within the four treatment arms during the intervention time and follow-up period of the study. The mixed effects

[figure not shown]
models will use the change in bone health levels (NTx, BAP) during the study and during follow-up as the outcomes. The subject will be included as a random effect, and treatment arms, time, their interactions, hormone therapy, and baseline bone health levels will be included as fixed effects. Individual trial arms will be compared to each other and the interaction term between treatment and time is used to investigate whether the benefit of the intervention changes with time. **Because of the small sample size and the resulting low statistical power, these secondary analyses will be interpreted very cautiously and only used to aid in the design of a study for our future K07 application.**

7.1.6 Additional analyses will examine between group differences in the other outcome measures. These will include Physical Activity (ACLS and Pedometer), aerobic capacity (VO₂max treadmill test), muscular strength (handgrip dynamometry and 7-10 repetition maximum), and muscle mass (Bioelectrical Impedance).

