2.0 Objectives

Both the calcitriol and exercise arms are aimed at reducing fracture risk by maintaining proper bone density, thereby preventing osteoporotic/osteopenic conditions and increasing muscle mass. Both calcitriol and exercise are efficacious in maintaining proper bone health and muscle mass among the general population, but little research has been done on breast cancer patients and survivors. The combination of calcitriol and exercise, which function through different but similar mechanisms, could produce interactive effects in reducing fracture risk among breast cancer survivors.

Hypothesis: A combination of calcitriol 45 µg/week along with a structured home-based walking and progressive resistance exercise program will be efficacious in preventing bone resorption, as defined by NTx level, and in increasing bone formation, as defined by BAP level, among survivors of invasive breast cancer.

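### Section 7.0 first compares arms on NTx and BAP with an unadjusted t-test on change, and its ANCOVA neither names the baseline marker nor limits covariates to pre-randomisation values

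*Combined protocol and SAP*

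**What the plan says.** Section 7.0 names NTx and BAP as the primary measures and states that "the primary analyses will consist of calculating mean change scores (i.e., baseline assessment minus final assessment) and standard deviations for the two variables above". Paired t-tests within arms follow. For differences between arms it lists two methods. The first is a two-sample test on change: "An independent t-test will be used to calculate the difference between the baseline and end of trial value for both BAP and NTx", applied between arms. The second comes last: "ANCOVA models will be used for BAP and NTx with the addition of relevant covariates collected during the study". The section adds that "Results of these two analyses will be interpreted cautiously because of the limited sample size".

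Section 7.1.5, under secondary analyses, describes an exploratory mixed model for change in NTx and BAP in which "treatment arms, time, their interactions, hormone therapy, and baseline bone health levels will be included as fixed effects". It says that "Individual trial arms will be compared to each other" and that "these secondary analyses will be interpreted very cautiously and only used to aid in the design of a study for our future K07 application".

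No section lists the covariates for the section 7.0 ANCOVA, and none says which between-arm analysis takes precedence.

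**The concern.** The pilot exists to supply estimates and SDs for a later grant (sections 1.6 and 7.0). Three features of section 7.0 work against that.

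- The first-listed between-arm comparison ignores the baseline value except by subtraction. Subtracting baseline is less efficient than regressing on it unless the regression slope of the week-12 value on baseline is 1. It also leaves the estimate exposed to chance baseline differences. Section 4.1.1 describes blocks of 8 and states no stratification factor, and section 3.8 lets hormone therapy continue, so balance on baseline turnover is left to chance.
- The ANCOVA wording does not fix the adjusted estimate before data are seen. Variables gathered in the study include baseline data. They also include, per the section 8.0 schedule, serum 1,25-dihydroxyvitamin D and supplement use at day 5, week 6 and week 12, and the week-12 pedometer reading. Treatment may change these, and adjusting for them could remove part of its effect.
- The change-score SD alone does not let the next study size a baseline-adjusted comparison. Section 7.1.5 plans correlations for the secondary variables, but no section plans them for NTx or BAP.

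**Working it through.** **The plan's own figure.** Section 7.2.1.1 claims 80% power for a 40% effect size without defining the metric. At a two-sided 5% level (assumed; none is stated), a four-group ANOVA F test with Cohen's f = 0.40 and 72 women has 79.9% power, which reproduces the claim. A two-arm t-test with d = 0.40 and 18 per arm has 21.5%. Nothing below depends on that figure.

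**Inputs.** 18 women per arm (sections 4.1.2 and 7.2.1; section 1.6 gives a total of 54 instead). Two-sided 5%, 80% power, no dropout. Let r be the correlation between baseline and week 12, and k the week-12 SD divided by the baseline SD. The documents give neither r nor k, so both are assumed and shown as ranges. Units are change-score SDs.

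**Variance ratio.** In units of the baseline variance, the change score has variance 1 + k² − 2rk, and the ANCOVA residual has k²(1 − r²). Their ratio is

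q = k²(1 − r²) / (1 + k² − 2rk), which is (1 + r)/2 when k = 1.

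**Detectable pairwise difference and 95% half-width.** For the t-test the SE is √(2/18) = 0.333 on 34 df. By noncentral t the detectable difference is 0.961, and the half-width is 0.677. For a four-arm ANCOVA with baseline and one hormone-therapy term, the df are 72 − 6 = 66 and the SE is 0.333√q. With k = 1:

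| r | q | variance cut | detectable | half-width |
|---|---|---|---|---|
| 0.3 | 0.65 | 35% | 0.764 | 0.537 |
| 0.5 | 0.75 | 25% | 0.821 | 0.576 |
| 0.8 | 0.90 | 10% | 0.899 | 0.631 |
| 0.9 | 0.95 | 5% | 0.924 | 0.649 |

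**What is not baseline adjustment.** With q = 1, moving from 34 to 66 df alone takes 0.961 to 0.948, a gain of about 0.014 from pooling four arms.

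**Sensitivity to k.** At k = 0.8 the variance cut is 50%, 43% or 36% for r = 0.3, 0.5 or 0.8, and the detectable difference is 0.672, 0.716 or 0.758. At k = 1.25 the cut is 22%, 11% or 0%, and the difference is 0.839, 0.896 or 0.948. The zero is exact: 1.5625 × 0.36 = 0.5625, and 1 + 1.5625 − 2.0 = 0.5625.

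**If only 54 women enrol** (13 to 14 per arm), with r = 0.5 and k = 1: 1.15 to 1.10 for the t-test against 0.97 to 0.94 for ANCOVA.

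**Simulation check** (6,000 trials, 18 per arm, r = 0.5, k = 1, true difference 0.82): power 66% for the t-test and 78% for the ANCOVA. The mean simulated ANCOVA half-width was 0.584, close to the formula's 0.576.

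**Chance imbalance.** The SD of the baseline difference between two arms of 18 is √(2/18) = 0.33 baseline SDs. With k = 1, a baseline difference δ moves the change-score estimate by −(1 − r)δ. A one-SD imbalance therefore shifts it by 0.5 × 0.333 = 0.17 baseline SDs at r = 0.5 and 0.3 × 0.333 = 0.10 at r = 0.7. Simulated slopes on the imbalance were −0.51 and −0.30 for change, and about 0 for ANCOVA.

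**Unequal arm SDs.** At r = 0.5 with k = 1.25 in the two arms compared and 0.8 in the other two (assumed), 95% intervals from a pooled-variance four-arm ANCOVA covered about 90%. HC3 standard errors restored about 95%, and the two-arm t-test also held about 95%.

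**The case against.** The strongest reply is that most of what is asked for is already there. Section 7.1.5 puts baseline marker level and hormone therapy in a model that compares arms, and an ANCOVA for both markers is planned. ANCOVA is often taken to include the baseline value, and the wording can be read as covariates added to it. No between-arm test is declared confirmatory, and the plan promises caution. Baseline SD, final SD and correlation could be computed later, since section 8.2 permits post hoc use of the data.

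Much of this stands, and it rules out three stronger readings that a reader might infer:

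- That the t-test is biased or invalid. It is neither under randomisation; it is less efficient.
- That no baseline-adjusted comparison is planned. One is, at exploratory rank.
- That the plan intends to adjust for post-randomisation variables. It proposes none; it only fails to exclude them, so any harm depends on the covariates chosen.

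What remains is that no text names the ANCOVA covariates or says which between-arm result leads, and cautious interpretation does not recover precision. The mixed model does not wholly fill the gap. Its outcomes include change during follow-up, but the section 8.0 schedule ends at week 12. It can, however, use the week-6 marker values in that schedule, which a week-12 ANCOVA does not.

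It is also fair to say that the size of the gain rests on assumed r and k and can be close to nothing.

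**Conclusion.** The point holds as one of rank and wording, with a concrete and cheap better method available; it should be changed, but it is not a flaw that invalidates the pilot. The text reading is certain. The size is conditional: over r from 0.3 to 0.9 with equal SDs, the variance saved runs from 35% down to 5%, and at r = 0.8 with an SD ratio of 1.25 there is no variance gain at all. These figures assume 18 evaluable women per arm, a two-sided 5% level, a common SD ratio across arms and model-based standard errors. They show what could be gained and do not predict it for these markers.

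**What to change.** In section 7.0:

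1. Make the lead between-arm analysis an ANCOVA of week-12 NTx, and separately of week-12 BAP, on that marker's baseline value, four-level treatment arm and baseline hormone therapy.
2. State that only covariates measured before randomisation may enter, and list any others in advance.
3. Report the pairwise arm differences (six per marker) with 95% CIs from heteroscedasticity-robust (HC3) standard errors, labelled as estimates and not tests.
4. Keep mean changes, SDs and paired changes as descriptive summaries.
5. Add each marker's baseline SD, week-12 SD and baseline to week-12 correlation, so that the later grant need not assume them.

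The cost is SAP wording and a few lines of code, with no new visits or samples. There are two downsides. The gain is small if the correlation is high. A pooled-variance version would give intervals that are too narrow for some pairs if arm SDs differ, which is why robust errors are specified.

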7.2 Sample Size

7.2.1 Seventy-two women (18 women per treatment arm) were selected as an adequate size to provide pilot data for subsequent studies.

7.2.1.1 Based on the enrollment numbers above, the study will be able to detect a 40% difference in effects size between bone resorption and formation with 80% statistical power between the groups. Below is a graph of various effect sizes and the corresponding statistical power.

7.2.2 Based on a discussion with breast cancer clinicians at the University of Rochester Medical Center about patient volume and projecting an accrual rate of 50%, it will take approximately ten months to enroll 72 women.

8.0 Records to be Kept

Procedure	Time Since Randomization			
	0	5 Days	6 Weeks	12 Weeks
Eligibility Interview	+			
Informed Consent	+			
Medical History	+		+	+
Assess Supplement Use	+	+	+	+
Blood CBC Levels	+	+	+	+
Serum 1, 25 OH ₂ D ₃ Levels	+	+	+	+
Bone Biomarkers	+		+	+
On Study Data (Demographics and Clinical Data)	+			+
Phone call reminders	Weekly	Weekly	Weekly	Weekly
Toxicity monitoring	+	+	+	+
Daily Diary	Daily	Daily	Daily	Daily
Functional Assessment of Chronic Illness Therapy (FACIT) (28-item QOL measure & 13-item fatigue subscale)	+			+
Brief Fatigue Inventory (BFI) (Severity of fatigue and level of interference in activities of daily living - 9 items)	+			+
Symptom Inventory (13-item symptom rating scale)	+			+
VO2max Treadmill Test	+			+
Aerobic Center Longitudinal Study Physical Activity Questionnaire (ACLS) (15-item physical activity history measure)	+			+
Pedometer	+			+
Tandem Walk Test (TWT)	+			+
Handgrip Dynamometer	+			+
7-10 Maximum Repetition	+			+
Bioelectrical Impedance Analysis	+			+

8.1 All hardcopy research records will be stored onsite in the University of Rochester Medical Center, in the Behavioral Medicine Unit of the James P. Wilmot Cancer Center. The Cancer Center is secured by electronic key cards. Offices within the Cancer Center are again secured by key and data is kept in locked file cabinets. Electronic research records are stored on the University of Rochester Medical Center's password secured and firewall protected networks. These are the same methods of security used for patient medical records. Human serum samples and biopsy samples are stored in locked freezers, within locked and alarmed laboratories that are accessible by key codes and electronic card swipes. All study data will be kept for a period of 10 years after the study and all reports and publications are complete.

8.2 All data (information, human blood samples, and human tissue samples) collected for the current study will be used in post hoc analyses as appropriate. No blood or biopsy samples will be banked. The patient is provided the opportunity to be contacted for future research studies in the informed consent. The patient's individual research record will not be shared with their treating physician, unless they provide consent or the patient's treating physician is a study physician, in

which case they will have access to study data as a study co-investigator. Overall study results will be presented to participants, faculty and staff at the University of Rochester Medical Center after completion of the study. Study results will be presented at professional meetings and published.

8.3 The study coordinator will assign a numerical Study ID to each participant once they have signed the consent form. All study forms and questionnaires will use this number and the participant's first, middle, and last initials as identifiers, to ensure data integrity. Other identifying information will not exist on these forms. A complete list of study participants with study ID, name, and contact information will be maintained separately. This linkage information will only be accessible to the study coordinator, study investigators, and the individual responsible for maintaining the database.

9.0 Patient Consent and Peer Judgment

9.1 Current, state, federal, and institutional regulations concerning informed consent will be followed.

